101 hypothesize that there is a moderate to strong positive correlation between the specificity of
102 the prompts and the quality of evidence-based health risk communication provided by LLMs.

103 3. Compare the evidence-based quality of responses generated by laypeople with varying levels
104 of informed prompting by comparing the quality of LLM responses based on prompts
105 generated by laypeople who provide varying levels of detail and information. We will assess
106 whether layperson-generated prompts result in more evidence-based responses than low-
107 informed prompts, but less so than moderately informed prompts.

108 RQ3: Are LLM responses generated by laypeople more evidence-based than those from low-
109 informed prompting, but less so than moderately informed prompting? We hypothesize that
110 Layperson-generated prompts produce more evidence-based responses compared to low-
111 informed prompts, but less so than moderately informed prompts that include about 50% of
112 key health decision-making information.

113 4. Evaluate the impact of a minimal boosting intervention on the quality of LLM responses by
114 assessing whether a minimal boosting intervention—where users are encouraged to provide
115 more specific prompts by considering the consequences of their health decisions—can
116 improve the evidence-based quality of LLM responses.

117 RQ4: Does a minimal boosting intervention increase evidence-based responses? We
118 hypothesize that reminding users to consider the consequences of their choices will lead to an
119 increase in evidence-based responses, improving the overall adherence of LLM outputs to
120 guideline-based communication standards.

121 5. Test the digital native hypothesis: RQ5: Without boosting intervention, digital natives (defined
122 as participants under 30 years of age) do not prompt a higher quality of LLM responses than
123 people from the age of 30 years and more.

124 **Trial Design**

125 The study is divided into two phases. Phase 1 uses a content analysis design to evaluate LLM responses
126 to standardized prompts. Phase 2 is a randomized between-subjects experiment with a 1:1 allocation
127 ratio, comparing standard prompting (control group) and enhanced prompting (intervention group).
128 Each group will interact with LLMs under similar conditions, but with differing levels of instruction
129 specificity.

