130 Given that this study is entirely web-based, there are no onsite requirements for integrating the AI
131 intervention into the trial setting. All interactions with the LLMs will occur remotely, facilitated through
132 the SoSci Survey platform, hosted by the University of Potsdam. The integration of the AI systems (Open
133 AI ChatGPT, Google Gemini, and Mistral AI Le Chat) is managed through an API, ensuring seamless
134 communication between the survey platform and the LLMs.

135 For offsite requirements, participants will need access to a digital device (computer, tablet) with a
136 stable internet connection to interact with the LLMs and complete the survey.

137 There is no need for any physical infrastructure or on-premises installations, as the entire intervention
138 process, from user prompts to LLM responses, will be executed in the cloud through secure, encrypted
139 connections.

140 **Methods**

141 This protocol was developed in adherence to the Guidelines for clinical trial protocols for interventions
142 involving artificial intelligence: the SPIRIT-AI extension.¹⁵

143 **Phase 1: Systematic Evaluation of LLM Responses to Predefined Prompts**

144 In the first phase of the study, we will systematically assess the quality of outputs generated by
145 OpenAI's ChatGPT, Google Gemini, and Mistral AI. The LLMs will respond to a set of predefined,
146 standardized English-language prompts related to BC and PC screening. These prompts will encompass
147 a range of typical patient inquiries, such as the risks and benefits of cancer screenings, the
148 interpretation of screening results, and the overall recommendation for undergoing screening. Each
149 LLM will respond to multiple iterations of the same prompts, allowing for an assessment of both
150 consistency and variability in the responses.

151 In total, six (decision preparation elements) times three distinct (in specificity varied) prompts will be
152 repeated 20 times across three LLMs and two screening topics, resulting in 2,160 total responses to be
153 scored. An additional scoring across six prompts (full decision preparation) will be based on nine
154 evaluation criteria of the compliance with context information standards (e.g. declaration of conflict of
155 interest). Each LLM response will be evaluated against predefined quality metrics, by independent
156 human raters using the validated MappInfo tool for the evidence-based quality assessment of digital

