157 health information¹⁶ and a new checklist derived from the Guideline for the Development of Evidence-
158 based Patient Information². This process will help identify patterns of strengths and weaknesses in how
159 LLMs communicate crucial health information.

160 **Phase 2: User-Generated Prompts and Evaluation with a Minimal Boosting Intervention**

161 The second phase of the study shifts from predefined prompts to user-generated prompts to explore
162 how laypeople's input affects the quality of LLM-generated health information. In this phase,
163 participants will be asked to generate their own prompts regarding breast and prostate cancer
164 screening. Participants will be randomized into two groups:

165 Control group: Participants will generate prompts with no specific guidance, reflecting a typical
166 layperson’s inquiry based on their own knowledge or concerns.

167 Intervention group: Participants will receive the minimal intervention (boosting) - a brief premise for
168 an evidence-based search: “Please consider the OARS rule: You need to know your options, the
169 advantages and risks of each, and how steady they are to happen.”, which implies simple instructions
170 encouraging them to consider the possible consequences of their health decisions and to provide more
171 specific, detailed prompts.

172 We will follow a similar approach to Phase 1, using predefined quality metrics to assess the responses.
173 Furthermore, this phase will analyze whether the boosting intervention improves the overall quality of
174 LLM responses by increasing the specificity and relevance of the user-generated prompts. Specifically,
175 the evaluation will focus on two key aspects: (1) the proportion of evidence-based responses,
176 measuring how often LLMs provide information aligned with established guidelines; (2) the impact of
177 the boosting intervention, determining whether simple guidance leads to significant improvements in
178 LLM outputs compared to unguided prompts.

179 **Analysis**

180 Phase 1:

181 Descriptive statistics will be used to summarize the quality scores of the LLM responses across the
182 different levels of prompt specificity. The mean scores with standard deviations will be calculated for
183 each LLM and prompt category. Additionally, the percentage of responses meeting the predefined
184 evidence-based criteria will be computed. We test the assumption of prompt specificity and explore

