185 potential differences between LLMs with the help of ANOVA across repetitions. Two independent
186 researchers will code the data. Interrater reliability will be assessed using Cohen’s kappa coefficient to
187 evaluate agreement between the coders. Any discrepancies will be resolved through consensus
188 discussions to ensure consistent and accurate evaluation.

189 Phase 2:

190 Descriptive statistics will be calculated for the demographic variables gender, age, and education, as
191 well as for LLM usage frequency, prior experience, and preference for shared decision-making.

192 The primary analysis will focus on comparing the quality of LLM-generated responses across groups
193 using inference statistical methods for assessing differences between participants assigned to the
194 prompting conditions (independent variable). To evaluate the responses (the dependent variable) the
195 responses will be coded using two predefined scales to assess its adherence to evidence-based (EB)
196 health communication standards and pooled additionally (so, three dependent variables for
197 independent analyses). The coding will be based on the MappInfo tool for the evidence-based quality
198 assessment of digital health information¹⁶ and the Guideline for the Development of Evidence-based
199 Patient Information². The coding will be done by two independent raters, and inter-rater reliability will
200 be assessed using Cohen’s kappa. Any discrepancies between raters will be resolved through discussion
201 and consensus. The code book will be provided in the appendix of the final study.

202 Secondary analyses will include a statistical test based on age split (<30 vs 30+ years) on the difference
203 in the quality of LLM responses prompted by participants of the control condition and there will be an
204 assessment of participant preferences for informed decision-making processes and their experiences
205 with LLMs, using descriptive statistics and mean comparisons. A subgroup analysis will explore
206 potential differences in responses based on demographic characteristics.

207 All statistical tests will be conducted at a significance level of $p < .050$ (and adjusted downwards
208 according to Bonferroni procedure for multiple testing), and effect sizes will be calculated to determine
209 the meaning of findings. Results will be presented in detail with supporting tables and figures.

210 **Inclusion Criteria**

211 Phase 1, LLMs:

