312 an API within SoSci Survey, and LLM providers do not have access to the study data. Payment processing
313 is managed entirely by prolific.co, and no financial data is collected or stored on our end. Additionally,
314 no names, addresses, birth dates, or IP addresses will be recorded. We will not record the recruitment
315 IDs generated by prolific.co, and due to the large number of simultaneous participants and the
316 variability in time between recruitment and survey completion, it will not be feasible to link
317 questionnaire responses with recruitment IDs.

318 The anonymized research data will initially be stored on a password-protected account under the
319 control of the project lead on the SoSci Survey server (hosted by the University of Potsdam). For further
320 analysis, the data will be transferred to password-protected computers under the supervision of project
321 team members at the Harding Center for Risk Literacy. Prolific will not have access to the research data
322 at any point.

323 **Statistical Methods**

324 Data will be analyzed using descriptive statistics and inferential statistical tests, including t-tests and
325 ANOVA for group comparisons, and linear regression models for more detailed analyses of prompt
326 specificity effects. All statistical tests will be conducted at a significance level of $p < 0.05$, and effect sizes
327 will be calculated to determine the practical significance of findings.

328 **Harms**

329 No physical or psychological risks are anticipated for participants. Anticipated survey completion time
330 is six minutes. Participation is entirely voluntary, and participants can withdraw at any time.

331 Errors of the used LLMs will be identified through content analysis conducted by independent human
332 raters using predefined quality metrics, and categorized based on their nature and impact on the
333 reliability of the information provided. The errors will then be analyzed to determine patterns of LLM
334 performance issues. If errors are not analyzed in specific instances, it will be due to limitations in the
335 scope of the study, such as focusing primarily on guideline adherence rather than linguistic or technical
336 issues outside the study's objectives.

337 **Monitoring**

338 The study will be monitored by the research team at the Harding Center for Risk Literacy. Regular audits
339 will be conducted to ensure compliance with the study protocol and data management procedures.

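### RQ2 claims a positive relation of at least moderate strength between prompt specificity and quality, but the test assigned to it is an ANOVA whose overall F shows neither sign nor strength

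*Protocol*

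**What the plan says.** Objective, item 2 (RQ2): the authors "hypothesize that there is a moderate to strong positive correlation between the specificity of" the prompts and the quality of the risk communication. The claim has a direction and a strength. No numerical cut-off is given.

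Methods, Phase 1: the design is "six (decision preparation elements) times three distinct (in specificity varied) prompts will be" "repeated 20 times across three LLMs and two screening topics, resulting in 2,160 total responses to be" scored. Specificity is therefore a three-level factor.

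Analysis, Phase 1: "We test the assumption of prompt specificity and explore" "potential differences between LLMs with the help of ANOVA across repetitions". This is the only sentence in the protocol that says how the specificity hypothesis is tested. The same section promises means and standard deviations for each model and prompt category.

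Analysis, Phase 2 (closing paragraph): the nominal level is 0.05, adjusted downwards "according to Bonferroni procedure for multiple testing), and effect sizes will be calculated to determine" what the findings mean. The type of effect size is not stated.

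Statistical Methods: the methods listed include "ANOVA for group comparisons, and linear regression models for more detailed analyses of prompt" specificity. The regression is not tied to RQ2 or to Phase 1.

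**The concern.** The hypothesis and its test answer different questions. RQ2 asks whether quality rises with specificity, and by at least a moderate amount. The overall F asks only whether the three level means are all equal. It can reject when quality falls with specificity, when the middle level is worst, or when the rise is real but trivial.

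With 2,160 scored responses, rejection is likely for almost any pattern of differences. The protocol does not say what besides a significant test is needed before RQ2 counts as supported. It also names three approaches (correlation in the hypothesis, ANOVA in the Phase 1 analysis, regression under Statistical Methods) without making one decisive, so the choice could be made after the results are seen.

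**Working it through.** **Inputs from the protocol.** Six elements, three specificity levels, 20 repetitions, three models, two topics; nominal alpha 0.05.

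**Assumptions, not in the protocol.** Scores normal with SD 1; responses independent; effects in SD units; levels coded -1, 0, 1. The Bonferroni level is illustrated as 0.05/3, because the number of tests is not stated.

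**1. The plan's own count.** 6 × 3 × 20 × 3 × 2 = 2,160, as stated. Per level: 2,160 / 3 = 720. The overall F has 2 and 2,157 degrees of freedom.

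**2. Middle level worst, correlation zero.** Level means 0, -0.2, 0; grand mean -0.0667.
- Sum of squared deviations: 0.0667² + 0.1333² + 0.0667² = 0.0267.
- Noncentrality: 720 × 0.0267 = 19.2.
- The critical F is 3.00, and power from the noncentral F is 0.981. At 0.05/3 the critical F is 4.10 and power is 0.951.
- The linear contrast is (-1)(0) + (0)(-0.2) + (1)(0) = 0, so there is no linear relation.

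**3. Reversed gradient.** Level means 0.2, 0, -0.2.
- Sum of squared deviations: 0.04 + 0 + 0.04 = 0.08. Noncentrality: 720 × 0.08 = 57.6. Power is above 0.999.
- The correlation averages -0.16 in simulation. The F rejects almost surely although RQ2 is wrong in sign.

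**4. Smallest significant effect.** Eta squared = 2F / (2F + 2,157).
- At alpha 0.05: 6.00 / 2,163.00 = 0.0028, square root 0.053.
- At 0.05/3: 8.20 / 2,165.20 = 0.0038, square root 0.062.

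**5. What moderate would require.** For a step of s SD per level, r² = (2s²/3) / (2s²/3 + 1), so s = √(1.5 r² / (1 - r²)).
- r = 0.3 (an assumed reading of moderate): s = √(1.5 × 0.09 / 0.91) = 0.39 SD per level.
- r = 0.5: s = √(1.5 × 0.25 / 0.75) = 0.71 SD per level.
- An r of 0.3 means r² = 0.09, about 32 times the smallest significant eta squared (0.09 / 0.0028).

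**6. Overall F against a directed slope.** 2,000 simulated data sets, 720 per level, two-sided 0.05.

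| Level means | Mean r | F significant | Positive slope significant |
|---|---|---|---|
| 0, -0.2, 0 | 0.00 | 97.8% | 2.3% |
| 0.2, 0, -0.2 | -0.16 | 100% | 0% |
| 0, 0.1, 0.2 | 0.08 | 93.6% | 97.0% |

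The slope separates the three patterns by direction; the F does not. The last row shows that even a significant positive slope does not establish moderate strength, which is why an estimate with its interval and a cut-off are also needed.

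**The case against.** The strongest reply is that ANOVA is not the only method named. Statistical Methods lists linear regression for specificity effects, and a slope has a sign and a size. Nor does the text exclude a linear contrast within the ANOVA, and the coding of contrasts is the kind of detail a statistical analysis plan usually supplies. Level means and effect sizes are promised, so a careful reader would see a reversal. All of this stands, and it limits the point. But the sentence that assigns the test names ANOVA, the regression is offered as an addition, and nothing links means or effect sizes to the RQ2 conclusion. A usual ANOVA effect size such as eta squared has no sign.

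The percentages depend on independence. Repeats of one prompt are probably correlated. If the 12 prompts per level (six elements × two topics) were the units, with the same means and SD 1, the power in step 2 would be about 7%; the prompt-level SD is unknown. How often a misleading rejection would occur is therefore uncertain. That the F has no direction does not depend on it.

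A reader might infer three stronger things that the protocol does not support:
- **RQ2 requires strictly ordered means.** It claims a positive correlation, which is compatible with a plateau.
- **The overall F wastes important power.** For the effects RQ2 expects (assumed r of 0.3 or 0.5) and 2,160 independent responses, both tests have power of about 100%.
- **RQ3 collapses with RQ2.** RQ3 makes its own comparisons, and no passage makes it depend on the Phase 1 F. If the order of low and moderate failed, RQ3 would simply not be supported.

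**Conclusion.** The point stands in limited form. The protocol states a directed hypothesis with a claimed strength and assigns it a method whose overall test can confirm neither. This is more than a detail left for later, because the protocol itself made the choice. It would be too strong to say that the plan has no means of examining direction, since regression is named; what is missing is its status as the deciding test.

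Under the independence assumption, the F rejects with about 98% power at zero correlation when the middle level is worst by 0.2 SD, and is significant at an eta squared of about 0.003. The effect patterns are assumed, since the protocol gives none for Phase 1. The consequence is confined to RQ2, in a phase without human participants; the randomised comparison in Phase 2 is not affected. The change is worth making because it costs almost nothing.

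**What to change.** In the Phase 1 analysis, name one directed test with one degree of freedom for RQ2: a linear contrast, or the regression slope on the ordered specificity levels, with model, topic and element as factors. State how the levels are scored. RQ3 gives a share of key information (about half) only for the moderate level, so either set the others or use equally spaced scores. Count direction as supported only if the slope is positive and significant.

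Report the correlation with its confidence interval, and fix in advance the cut-off for moderate and how the estimate or interval is judged against it. Keep the overall ANOVA for the exploratory comparison of models. Bring Objective item 2, the Phase 1 analysis and Statistical Methods into line.

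The cost is a few sentences and no new data. The downside is that a non-monotone pattern would show only in the level means, which the plan already reports.

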245 responses will be excluded.

246 Phase 2, Participants:

248 The exclusion criteria for selecting the Participants in the study will be the following:

- 249 - Health Professionals: Individuals with professional expertise in healthcare, particularly in
250 cancer screening or health communication, will be excluded to avoid bias and ensure that
251 participants reflect the general lay population.
252 - Previous Experience with LLM Studies: Participants who have taken part in similar studies
253 involving LLMs will be excluded to prevent familiarity with the technology from influencing the
254 results.

255 **Procedure and material**

256 Phase 1:

257 Researchers will prompt LLMs via API and collect the responses.

258 Phase 2:

259 Participants will receive a brief introduction outlining the study's purpose, which involves interacting
260 with one of three LLMs [OpenAI ChatGPT (gpt-3.5-turbo)¹⁷, Google Gemini (1.5-Flash)¹⁸, or Mistral AI
261 Le Chat (mistral-large-2402)]¹⁹, all preset as a "helpful assistant" to obtain health information of either
262 BC or PC screening. Following informed consent, participants will be asked to provide basic
263 demographic details such as gender, age, and education level through a questionnaire interface built
264 with SoSci Survey. They will then be given the choice to receive information about either BC or PC
265 screening. Participants will engage with the chatbot by entering their queries (prompts) through the
266 LLM's API, and the generated responses will be collected alongside the prompts for systematic analysis.
267 At the end of the session, participants will be asked about their frequency of LLM usage, their prior
268 experience with such models, and their perspectives on how an informed decision-making process
269 should ideally be conducted for them, by choosing one from four options.

270 A pre-test with n=20 participants will be conducted to verify the effectiveness of the randomization
271 procedures, ensuring balanced group assignment, the technical functionality of the survey platform
272 and its integration with the LLM APIs. Additionally, the average completion time will be measured and
273 potential issues related to participant burden will be identified. Feedback on user experience will be
274 collected to address any usability concerns. Based on these findings, necessary adjustments will be
275 made at the protocol for the main trial.

276 **Tests and Outcomes**

277 Primary Outcome:

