278 Expert scoring of how evidence-based LLM communication is (mappInfo tool in addition to a novel
279 score based on the guideline EB health information)

280 Secondary Outcome:

281 Self-reported use and experience with LLM; preference in shared decision-making

282 **Sample Size**

283 Phase 1:

284 There are no human participants involved.

285 Phase 2:

286 To analyze a moderate ANOVA main effect (partial eta squared = .06) comparing two between-subjects
287 conditions (with and without intervention), we are aiming for a minimum sample size of n= 237

288 participants. To ensure a representative sample reflecting the simplified census data of Great Britain in
289 terms of sex, age, and ethnicity, we will recruit $n = 300$ participants from a diverse pool via Prolific²⁰.

290 **Recruitment**

291 Participants will be recruited via the online platform Prolific²⁰.

292 **Assignment of Interventions**

293 Participants will be assigned to either the control group or the intervention group via block
294 randomization. In the intervention group, participants will receive additional instructions designed to
295 improve the quality of the prompts they generate for the LLMs.

296 **Allocation**

297 To achieve a balanced distribution of participants across the study groups, we will employ a block
298 randomization (1:1 allocation ratio) with the BLOCKRAND() function in SoSci Survey. The assignment
299 is concealed by this function.

300 **Blinding**

301 Participants and researchers will be blinded to both the assigned LLM and the type of prompting
302 instructions to prevent any bias in interaction and response evaluation. Coding will happen
303 independently by two researchers.

304 **Data Management**

305 Data will be collected via the SoSci Survey platform, and all datasets will be anonymized and stored
306 securely on password-protected servers to ensure participant confidentiality. Contact details will not
307 be collected, as Prolific—responsible for participant recruitment—operates with an anonymized data
308 collection model. Participant demographic data, such as gender and age, will be collected separately
309 within the study, despite these being part of the quota set by Prolific.

310 Data handling is fully anonymized. Prolific manages recruitment, while SoSci Survey, hosted by the
311 University of Potsdam, handles the questionnaires. Communication with the LLMs is facilitated through

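### Phase 2 names no LLM factor in its primary comparison and describes no balancing of the three LLMs across arms, so a nearly free gain in precision is not secured

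*Protocol*

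**What the plan says.** - **Exposure to LLMs.** Procedure and material, Phase 2, has each participant interact "with one of three LLMs [OpenAI ChatGPT (gpt-3.5-turbo)¹⁷, Google Gemini (1.5-Flash)¹⁸, or Mistral AI" Le Chat. The participant chooses breast or prostate cancer screening as the topic. The Blinding section speaks of an assigned LLM, so an assignment exists, but no section says how it is made.
- **Allocation.** Under Assignment of Interventions: "Participants will be assigned to either the control group or the intervention group via block" randomisation. The Allocation section gives a 1:1 ratio and the SoSci Survey block function. Neither section mentions LLM.
- **Primary analysis.** Analysis, Phase 2, compares quality "using inference statistical methods for assessing differences between participants assigned to the" prompting conditions, which it labels the independent variable. No other factor is named. The outcome is analysed in three forms: two scales and their pooled score.
- **Sample size.** "To analyze a moderate ANOVA main effect (partial eta squared = .06) comparing two between-subjects" conditions; "we are aiming for a minimum sample size of n= 237"; and then "we will recruit $n = 300$ participants".
- **Statistical Methods** lists t-tests, ANOVA and linear regression, with no list of factors or covariates.
- **LLM differences** are explored by ANOVA in Phase 1. The Phase 2 subgroup analysis is demographic.

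**The concern.** The score is a property of a response, and the response comes from one of three different models. Phase 1 takes this seriously: it crosses prompts with LLM and summarises scores by LLM. The Phase 2 primary comparison, as written, does not mention LLM in either the allocation or the model.

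Two consequences follow if that reading is carried out literally. Differences in average quality between LLMs stay in the residual variance against which the boosting effect is tested. The mix of LLMs may also differ between arms in the realised sample. Both concern precision. The model can still be settled in an analysis plan, but the allocation is fixed once the survey goes live and no later document can change it.

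**Working it through.** **1. The plan's own figure.** Partial eta squared .06 gives f² = .06/.94 = 0.0638, f = 0.253 and, for two equal arms, d = 2f = 0.505. The minimum of 237 cannot be reproduced from the protocol, because neither the power nor the number of tests in the Bonferroni correction is stated. With the noncentral F (1 numerator df, λ = N·f²), N = 237 has 97.2% power at alpha .05. At .05/3 = .0167 it has 92.9%. The divisor of three is my assumption, taken from the three dependent variables. At N = 300 the powers are 99.2% and 97.5%.

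**2. Standard error of the arm effect.** Let R² be the share of within-arm score variance explained by LLM. The protocol gives no value, so a range is shown. With LLM balanced across arms, and ignoring the two degrees of freedom used:

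SE ratio (adjusted to unadjusted) = √(1 − R²); equivalent N = 300/(1 − R²).

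| Assumed R² | SE ratio | SE reduction | Equivalent N |
|---|---|---|---|
| .05 | .975 | 2.5% | 316 |
| .10 | .949 | 5.1% | 333 |
| .20 | .894 | 10.6% | 375 |
| .30 | .837 | 16.3% | 429 |

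**3. Chance imbalance.** Assume each participant receives an LLM independently with probability 1/3, and 150 participants per arm. The SD of the between-arm difference in one LLM's share is √[(1/3)(2/3)(2/150)] = 0.054. The 95% range is ±1.96 × 0.054 = ±0.107, or about 11 percentage points. If that LLM scored 0.5 to 1 SD away from the others (assumption), an imbalance at this limit would move the estimate by 0.107 × 0.5 = 0.05 to 0.107 × 1 = 0.11 SD. That is roughly 10 to 21% of the planned d of 0.505. This is an unlucky draw and not the expected case.

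**4. Power of the unadjusted test.** The least favourable reading is that .06 is already net of LLM, so the unadjusted test has f²(1 − R²):

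| Assumed R² | N = 300, alpha .05 | N = 300, alpha .0167 | N = 237, alpha .0167 |
|---|---|---|---|
| 0 | 99.2% | 97.5% | 92.9% |
| .10 | 98.5% | 95.9% | 89.9% |
| .30 | 95.4% | 89.4% | 80.0% |

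If .06 is instead the unadjusted effect, the R² = 0 row applies to the unadjusted test whatever LLM explains.

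**The case against.** The strongest reply is that the point rests largely on silence. The methods named include ANOVA and regression, no factor is excluded, and model terms are commonly left to an analysis plan, which is not at hand. The sample-size wording, a main effect with a partial eta squared, is compatible with a model that has further factors. This stands. A reader might infer that the trial will ignore LLM or has left its balance to chance, but the protocol says neither. LLM is not named in the primary comparison, and its assignment is not described. Nor does the protocol show that LLM variance is known to be present: Phase 1 sets out to explore it.

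A reader might also infer bias. Randomised arms keep the unadjusted comparison unbiased, and chance imbalance is already part of its standard error. The imbalance in step 3 is therefore another view of the same loss of precision and not a second harm.

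The power objection stands too. With 300 participants, power stays at about 89% or more for R² up to .30, even at the stricter assumed alpha.

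Two further extensions are tempting and not supported. The first is to adjust for topic outright. Topic is chosen by the participant, and the protocol does not say whether the choice comes before or after the OARS text. If it comes after, topic could itself be affected by the intervention. The second is to fault the late placement of the usage items ("At the end of the session, participants will be asked about their frequency of LLM usage, their prior" experience) and turn them into covariates. The protocol lists them as secondary outcomes and plans no adjustment for them. Asking them earlier could prime participants before they write their prompts, so the order is a trade-off and not an error.

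The reply does not answer the allocation point. How the LLM is assigned, and whether arms are blocked within it, belongs to the design.

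**Conclusion.** The point holds as a gap in precision and description. Only the prompting condition is named in the primary comparison, and blocking is described for two arms although three LLMs are in use. The avoidable loss is about 2.5 to 16% of the standard error if LLM explains 5 to 30% of score variance. Under independent 1/3 assignment, one LLM's share could differ between arms by about 11 percentage points (95% range) at N = 300. Both ranges rest on assumptions that the protocol neither supports nor contradicts. The comparison remains valid and adequately powered without the change. The change is worth making because it costs almost nothing and the allocation part must be settled before the survey opens.

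**What to change.** State in the Allocation section how the LLM is assigned. Run the block randomisation over the six arm-by-LLM cells, so that allocation is 1:1 within each LLM; with 300 participants that is 300/6 = 50 per cell. Name the primary model as an ANOVA with arm and LLM as main effects, test the arm effect, and show the arm-by-LLM results descriptively. Add chosen topic as a factor only if the survey has the topic chosen before the OARS text is shown, and state that order in the Procedure section. Leave the LLM-use items where they are.

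The cost is one survey setting, a sentence or two of text and two model degrees of freedom (residual df 296 instead of 298 at N = 300).
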